### 2. Prior treatment

- **Cyclophosphamide (Yes/No)** – categorical variable determining whether subjects have ever received any cyclophosphamide treatment, either IV or oral. Calculated from oral and IV cyclophosphamide variables; patients can receive either treatment or both. In incomplete cases the subject will be regarded as not having received the treatment specified.
- **Cumulative cyclophosphamide dose (g)** – continuous variable, sum of the Oral and IV cyclophosphamide doses (g); patients can receive either

treatment or both. In incomplete cases the subject will be regarded as not having received the treatment specified (i.e. dose = 0 g).

- **Rituximab or cyclophosphamide (Yes/No)** – categorical variable determining whether subjects have ever received any rituximab or cyclophosphamide treatment, either IV or oral. Calculated rituximab and cyclophosphamide variables; patients can receive either treatment or both. In incomplete cases the subject will be regarded as not having received the treatment specified.
- **Number of prior immunosuppressants (excluding glucocorticoids) (integer)** – a count of the number of prior immunosuppressants (excluding glucocorticoids) received by each subject. The following treatments are included: cyclophosphamide (Oral or IV), rituximab, azathioprine, methotrexate, mycophenolate mofetil, IVIG, anti-TNFs, and other immunosuppression listed in the Baseline Medical History Form. In incomplete cases the subject will be regarded as not having received the treatment specified. The variable will be reported both as categorical and continuous.

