**Table 5: ANCA Status**

		Anti-MPO		
		Positive	Negative	Not measured
Anti-PR3	Positive	Positive PR3 & MPO	Positive PR3	Positive PR3
	Negative	Positive MPO	Negative	Unknown
	Not measured	Positive MPO	Unknown	Unknown

Table 6: Details of formulas for derived variables

Variable name	Label	Type	Original variables (MACRO ShortCode)	Formula
MHDuration	Prior disease duration	Real	MHDat1, Visit1	Date difference (years)
HisANCA	Historical ANCA positivity	Category	MHEli1, MHEli2	See Table 4 for details
BLM_Score BLM_Score_cat	Total number of Body Systems affected	Integer/ Category	BLM_* variables	Sum
MHCycl	Total cyclophosphamide	Category	MHTre3, MHTre4	if either = 1 then => 1 (Yes) else => 0 (No)
MHCyclDose	Cumulative cyclophosphamide dose	Real	MHCyc1, MHIVC1	Sum
MHRitCyc	Previous treatment with rituximab or cyclophosphamide (either IV or oral)	Category	MHTre5, MHCycl	if either = 1 then => 1 (Yes) else => 0 (No)
MHImmN MHImmN_cat	Number of prior immunosuppressants	Integer/ Category	CumCyclo, MHTre5, MHTre6, MHTre7, MHTre8, MHTre11, MHTre12, MHImS1, MHImS2, MHImS3, MHImS4, MHImS5, MHImS6	Sum
BVASStatus	Disease status	Category	BVAS12a, BVAS12b, BVAS12c, BVAS12d	Hierarchical order, categories evaluated in order, from the most specific to the most general: 1. Remission 2. Severe flare 3. Limited flare 4. Persistent
CDAScore CDAScore_cat CDAScore_grp	Total CDA score	Integer/ Category	selected variables of CDA Form (see section 9.8)	Sum
CDADiff CDADiff_cat	Change in total CDA score between month 4 and month 12, month 24, month 36 & month 48. Change in total CDA score between	Integer/ Category	CDAScore	Difference

	month 24 and month 36 & month 48			
TreatRituxSum	Total rituximab dose (mg)	Real	TreatTotalRitux	Sum
TreatRituxPrctcol	Overall full rituximab treatment	Category	TreatAdmnProtcol	Yes if sum(TreatAdminProtocol="Yes")=5
TreatRituxMonths	Number of full rituximab infusions	Integer/Category	TreatAdmnProtcol	count(TreatAdminProtocol="Yes")
TreatMPredDose	Total IV methylpredniso(lo)ne dose (mg)	Real	TreatMPredDose	Sum
PredMean PredMean24	Average predniso(lo)ne dose (mg/day) - (Overall /Maintenance)	Real	FUp1aPredDose	Average If FUp1a1 then Fu1aPredDose=0
PredAUC PredAUC24	AUC of predniso(lo)ne dose (mg) - (Overall /Maintenance)	Real	FUp1aPredDose	Vertical step function, assumes month=30days

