### 11.3 Hypogammaglobulinemia

Hypogammaglobulinemia is defined as a value of IgG < 5 g/L measured at any stage of the trial (including visits occurring during the induction period). Frequency tables for hypogammaglobulinemia will be reported using the full analysis population and stratified by treatment arm and:

- a) Induction regimen (1A/1B)
- b) ANCA type (anti-PR3/anti-MPO)
- c) Relapse type (Severe/Non severe)
- d) Previous treatment with rituximab (Yes/No)
- e) Previous treatment with cyclophosphamide (Yes/No)
- f) Previous treatment with rituximab or cyclophosphamide (Yes/No)
- g) Baseline (Screening/Month 0) IgG (g/L).

A logistic regression analysis will be carried out to predict hypogammaglobulinemia, using the above as predictor variables. Individual univariate models and a multivariate model will be considered. Outcomes (Estimate, 95% CI and P-value) will be surmised in tabular form.

These analysis are to be considered exploratory only, as they were not specified in the protocol and the data is observational.

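### SAP 11.3: entering prior rituximab, prior cyclophosphamide and their union together makes the exploratory multivariate model an unlabelled interaction model with less precise drug coefficients

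*SAP*

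**What the plan says.** SAP 11.3 defines hypogammaglobulinaemia as an IgG below 5 g/L at any stage of the trial and lists seven variables, a to g. Three concern earlier drug exposure: d, "Previous treatment with rituximab (Yes/No"; e, "Previous treatment with cyclophosphamide (Yes/No"; and f, "Previous treatment with rituximab or cyclophosphamide (Yes/No". The list first serves to stratify the frequency tables. The section then turns it into a predictor list: "A logistic regression analysis will be carried out to predict hypogammaglobulinemia, using the above as predictor variables". It adds: "Individual univariate models and a multivariate model will be considered". Estimates, 95% confidence intervals and p-values are to be tabulated. No selection rule takes any of the seven out of the multivariate model. The section closes by calling the analyses exploratory, because the protocol did not specify them and the data are observational.

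SAP 9.2 (Prior treatment) describes f as a "categorical variable determining whether subjects have ever received any rituximab or cyclophosphamide treatment, either IV or oral" and notes that "patients can receive either treatment or both". SAP Table 6 gives its formula from the prior rituximab and prior cyclophosphamide variables: "if either = 1 then => 1 (Yes) else => 0 (No".

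**The concern.** On the plain reading, d, e and f all enter one model, although f is fully determined by d and e. The planned table would then show rows labelled as prior rituximab and prior cyclophosphamide whose multivariate coefficients are contrasts within a subgroup. The univariate rows with the same labels compare all exposed with all unexposed patients. A reader who sees the two differ would put the change down to adjustment for confounding, when part of it may come from the changed contrast.

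Precision is also lost, and with sparse cells a coefficient may not be estimable at all. Long-term safety of rituximab is a secondary objective and IgG below 5 g/L is a selected adverse event, so these rows are likely to be read.

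**Working it through.** The SAP states no figure for this model, so there is none to reproduce.

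**Inputs.** From the SAP: f is 1 if either d or e is 1 (Table 6); a patient may have had both drugs (9.2); 160 patients are to be randomised (section 7). Not in the documents, so assumed: prevalence of prior cyclophosphamide P(C) 60–85%; prevalence of prior rituximab P(R) 25–40%; R and C independent; no drug effects; baseline risk about 25% (intercept −1.1). Covariates a, b, c and g are left aside. The number of patients and the baseline risk cancel from the standard-error ratios.

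**Step 1: what the coefficients mean.** For two binary variables, f = d + e − d×e. Write the logit as β0 + βd·d + βe·e + βf·f. The four groups then have these logits:

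| Group | Logit |
|---|---|
| Neither drug | β0 |
| Rituximab only | β0 + βd + βf |
| Cyclophosphamide only | β0 + βe + βf |
| Both drugs | β0 + βd + βe + βf |

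Therefore:
- βd = both minus cyclophosphamide only, the rituximab effect among patients who also had cyclophosphamide;
- βe = both minus rituximab only, the cyclophosphamide effect among patients who also had rituximab;
- βf = minus the d-by-e interaction.

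The model has four parameters for four groups, as the explicit interaction model does, and the fit is identical.

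**Step 2: an illustration.** Take true log-odds effects, each in the absence of the other drug, of 0.7 (rituximab) and 0.5 (cyclophosphamide), with interaction −0.4. The model with f targets 0.7 − 0.4 = 0.3, 0.5 − 0.4 = 0.1 and +0.4. A simulated fit with 400,000 patients gave 0.29, 0.09 and 0.41. The model with d and e only gave 0.41 and 0.32, which corresponds to P(R) = 40% and P(C) = 70%. With the interaction set to zero, the model with f returned 0.70 and 0.50, the ordinary adjusted effects.

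**Step 3: loss of precision.** Let v = p(1 − p) be the outcome variance at common risk p.
- Cyclophosphamide with f: variance = (1/v)·[1/(N·P(R)·(1 − P(C))) + 1/(N·P(R)·P(C))] = 1/[N·v·P(R)·P(C)·(1 − P(C))].
- Cyclophosphamide without f: variance = 1/[N·v·P(C)·(1 − P(C))].
- The ratio is 1/P(R), so the standard error rises by 1/√P(R). By symmetry it rises by 1/√P(C) for rituximab.

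Over the assumed ranges:
- rituximab: 1/√0.85 = 1.08 to 1/√0.60 = 1.29;
- cyclophosphamide: 1/√0.40 = 1.58 to 1/√0.25 = 2.00.

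Worked case, N = 160, P(R) = 40%, P(C) = 70%. The groups are neither 28.8, rituximab only 19.2, cyclophosphamide only 67.2, both 44.8. With p about 0.25, v = 0.187.
- Rituximab: with f, √[(1/67.2 + 1/44.8)/0.187] = 0.45; without f, 0.37; factor 1.20.
- Cyclophosphamide: with f, √[(1/19.2 + 1/44.8)/0.187] = 0.63; without f, 0.40; factor 1.58.

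**Step 4: sensitivity.** Over a wider grid (P(R) 10–60%, P(C) 30–90%, R–C odds ratio 0.5, 1 or 2, no drug effects) the factors run from 1.03 to 2.27 for rituximab and from 1.17 to 4.14 for cyclophosphamide. With both log-odds effects at 0.7 they run from 1.03 to 2.22 and from 1.14 to 3.73.

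**Step 5: sparse cells.** By step 1 the cyclophosphamide coefficient rests on the both and rituximab-only groups. At P(R) = 25% and P(C) = 85%, rituximab only holds 160 × 0.25 × 0.15 = 6 patients, and neither holds 160 × 0.75 × 0.15 = 18. If nobody had both drugs, f = d + e. If everybody had at least one, f is constant. In either case one coefficient cannot be estimated.

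**The case against.** The strongest reply is that little depends on this model. The SAP calls it exploratory, and no primary or protocol-listed secondary endpoint, randomised comparison or trial decision uses it. Its stated aim is prediction, and a model with an interaction predicts perfectly well. The wording says only that a multivariate model will be considered, and the list also serves as stratifiers for frequency tables, where f belongs. Adjusted and univariate coefficients differ in any case. All of this stands as a limit on the consequence. It does not remove the problem: the stated predictor list includes f, no rule drops it, and a table of estimates and p-values by named predictor is planned.

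Three stronger readings are tempting, and the documents do not support them.
- A reader might infer that the drug coefficients stop measuring drug effects. Each still measures that drug's effect among patients who had the other drug, and equals the usual adjusted effect if there is no interaction. The documents give no evidence for or against one.
- A reader might take a doubling of standard errors as a property of this trial, or as a ceiling. It is what a 25% prevalence of the other drug implies under independence; the documents give neither the prevalences nor the association. Inclusion criterion 4 lists the two drugs among alternative earlier induction agents, so independence may well fail.
- A reader might blame a small group with neither drug. That group identifies the f coefficient. Other covariates aside, it does not drive the imprecision of d or e.

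**Conclusion.** The point holds as a minor, free improvement. The change in meaning is exact algebra and needs no assumption beyond the plain reading that all listed predictors enter the multivariate model. The size of the precision loss does rest on assumptions: about 1.1–1.3 times for rituximab and 1.6–2.0 times for cyclophosphamide at the assumed prevalences, with independence and no drug effects. For either drug the loss grows as the prevalence of the other falls. The drug coefficients differ from the ordinary adjusted effects only to the extent that there is an interaction on the logit scale. The primary analysis, the frequency tables, the univariate models and the overall fit of the multivariate model are not affected.

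**What to change.** Add one sentence to SAP 11.3: the combined exposure variable f is used for the frequency table and its own univariate model, and the multivariate model contains d and e without f. If a summary of any earlier exposure is wanted after adjustment, fit f in place of d and e as a separate model. If an interaction between the two drugs is of interest, enter the product term explicitly and label it and the conditional drug effects as such.

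Leaving f out averages over any interaction, which is a reason to state the choice in advance. The change needs no new data and no extra analysis effort. Tabulating the four exposure groups beforehand would show whether an interaction can be estimated.

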## 11.2 Adverse Events

In addition to all SAEs, the following selected adverse events (AEs) are being collected as part of the RITAZAREM trial:

1. Infections (all episodes requiring treatment with intravenous (IV) or oral antibiotics or infections that are commonly understood to be opportunistic)
2. Occurrence of hypogammaglobulinemia (IgG <5g/l)
3. Occurrence of hypogammaglobulinemia (IgG <3g/l)
4. An adverse event that results in a change in dose of trial IMPs (rituximab, azathioprine, methotrexate or mycophenolate mofetil (MMF))
5. An adverse event that results in the addition of a relevant concomitant medication (see section 13.3.1 for list)
6. An adverse event manifested by the occurrence of a relevant laboratory abnormality (see section 13.3.2 for list)
7. New malignancies

Infections are recorded using the Infection Form and entered in the MACRO database. Frequency tables for serious and non-serious infections with date of onset occurring in the maintenance phase will be reported using the safety population and stratified by induction regime. The number of patients with newly occurring IgG < 5g/L and newly occurring IgG < 3g/L will be reported. Additionally, counts of subjects and events for non-serious infections will be reported, grouped by High Level Group Term and Preferred Term based on the MedDRA code.

Individual listings of infections are reported to the DSMB and reviewed quarterly.

New malignancies are recorded using the New Malignancy Form and entered in the MACRO database. All instances of new malignancies detected during the maintenance phase will be reported as individual listings sorted per patient by site. The following detail will be reported:

- Treatment arm
- Malignancy Detection date
- Malignancy Diagnosis date
- Malignancy Site
- Malignancy Type
- Malignancy Reoccurrence
- Malignancy Treatment (Surgery, Radiotherapy, Chemotherapy, Other)
- Malignancy Associated with SAE (Yes/No)
- Malignancy Comments

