## 11.6 Clinical Laboratory Evaluations

Clinical laboratory tests will be performed at baseline (either at Screening or Month 0, taking the latest value if assessment were performed at both visits), and at each visit in the maintenance phase (months 4, 8, 12, 16, 20, 24, 27, 30, 36, 42 and 48). Measured values will be recorded in the Clinical Laboratory Tests Forms and entered

in the MACRO database. Data management will ensure that any missing values are due to the test not being performed (“Not measured” tick-box).

The following variables will be summarised in accordance with section 9 using the full analysis population. Missing values will be assumed to be “not measured” without cross-referencing the relevant tick-box.

- Clinical Labs
  - Haemoglobin (g/dL)
  - Platelets (cells x 10^9/L)
  - WBC (cells x 10^9/L)
  - ESR (mm/h)
  - Creatinine (µmol/L)
  - CRP (mg/L)
  - ALT (U/L)
  - AST (U/L)
- ANCA
  - Anti-PR3 (positive/negative)
  - Anti-MPO (positive/negative)
  - ANCA status – derived variable, details in section 1.1
- Lymphocyte markers
  - CD19 (cells x 10^9/L and %)
- Immunoglobulins
  - IgG (g/L)
  - IgM (g/L)
  - IgA (g/L)

Table 8 lists the preferred unit for reporting and the multiplicative conversion factor (CF) employed for those clinical labs collected in the CRF using different measurement units.

---

 Conversion factors taken from <http://www.scymed.com/en/smnxfd/smnxfdac.htm>

Table 8: Conversion factors

Variable	Original unit	CF	Reporting unit
Haemoglobin	g/L	0.1	g/dL
Haemoglobin	mmol/L	1.611344	g/dL
WBC	cells x 10  /mm 	1	cells x 10  /L
Creatinine	g/dL	88.42 x 10 	µmol/L
Creatinine	mg/dL	88.42	µmol/L
CRP	mg/dL	10	mg/L
CD19	cells x 10  /mm 	1	cells x 10  /L
CD19	cells/µL	0.001	cells x 10  /L
IgG	mg/dL	0.01	g/L
IgM	mg/dL	0.01	g/L
IgA	mg/dL	0.01	g/L

Laboratory values outside the ranges detailed in Table 8 will be considered un-physiological, and will be considered outliers and excluded from the analysis. All such values will be listed in a separate table (grouped by item, subject, and visit) and queried by the data manager.

Table 9: Physiological ranges for laboratory tests

Variable	Minimum	Maximum	Reporting unit
Haemoglobin	5	20	g/dL
Platelets	5	900	cells x 10  /L
WBC	1	40	cells x 10  /L
ESR	0	200	mm/h
Creatinine	30	1500	µmol/L
CRP	0	600	mg/L

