Figure 29: Forest plot of cox proportional hazards model – Tertiary endpoint.

Figure 30: Serious Adverse Events, forest plot of frequency and relative risk by treatment arm.

Figure 31: Non–serious infections, forest plot of frequency and relative risk by treatment arm.

Figure 32: Kaplan–Meier plot of SAE–free survival by treatment arm.

Figure 33–45: Boxplots by treatment arm of continuous clinical lab tests:  
Haemoglobin, Platelets, WBC, ESR, Creatinine, CRP, ALT, AST, CD19, CD19 (%), IgG, IgM, and IgA.

Figure 46–48: Stacked bar charts by treatment arm of discrete clinical lab tests:  
Anti–PR3, Anti–MPO, and ANCA status.

Figure 49: Alluvial plot of ANCA status by treatment arm, showing change from month 4 to month 24 and to month 36.

Figure 50: Bar charts of EQ–5D–5L questionnaire item's responses.

Figure 51: Boxplot of EQ–5D–5L index totals (VAS Health state, OTT utility score, and VAS utility score) by treatment arm.

Figure 52–54: Bar charts of PROMIS questionnaire item's responses (fatigue, pain, physical ability).

Figure 55: Bar chart of PROMIS questionnaire sub–totals by treatment arm.

Figure 56: Boxplots of PROMIS questionnaire sub–totals by treatment arm.

Figure 57: Boxplot of PROMIS questionnaire total score by treatment arm.

Figure 58–63: Bar charts of SF–36 questionnaire item's responses.

Figure 64: Boxplot of SF–36 questionnaire sub–totals by treatment arm.

Figure 65: Boxplot of SF-36 questionnaire PCS and MCS components by treatment arm.

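### The only model of IgG (SAP 11.3, exploratory) is an ever/never regression that counts pre-randomisation values and does not clearly include treatment arm, so the plan has no efficient between-arm comparison of IgG

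*SAP*

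**What the plan says.** SAP 11.3 sets the outcome: "Hypogammaglobulinemia is defined as a value of IgG < 5 g/L measured at any stage of the trial", and the sentence goes on to include visits in the induction period. Frequency tables are split by arm and by seven items: induction regimen, ANCA type, relapse type, prior rituximab, prior cyclophosphamide, prior use of either, and baseline IgG. Then: "A logistic regression analysis will be carried out to predict hypogammaglobulinemia, using the above as predictor variables". The section closes with a caveat: "These analysis are to be considered exploratory only, as they were not specified in the protocol and the data is observational".

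Other IgG outputs are descriptive. SAP 11.6 schedules laboratory tests at baseline and "at each visit in the maintenance phase (months 4, 8, 12, 16, 20, 24, 27, 30, 36, 42 and 48", lists IgG in g/L, and says "The following variables will be summarised in accordance with section 9 using the full analysis population". SAP section 13 adds "Boxplots by treatment arm of continuous clinical lab tests", with IgG among them. SAP 11.2 adds counts: "The number of patients with newly occurring IgG < 5g/L and newly occurring IgG < 3g/L will be reported".

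Long-term safety of rituximab is secondary objective 2 (Protocol 9.5.2, SAP 5.1.2). SAP 5.2.3 leaves the endpoint correlating rituximab levels with B cells and immunoglobulins to possible future analyses.

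**The concern.** IgG is measured repeatedly on a continuous scale, and the one model fitted to it keeps a single yes/no per patient. Within that model a fall from 12 to 5.1 g/L counts as no event, 4.9 and 2.0 g/L count the same, and timing, duration and recovery are lost.

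Three features of SAP 11.3 weaken it further as a comparison of arms:

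- A value below 5 g/L before randomisation makes the patient a case whatever the allocation, which dilutes any arm effect. Baseline IgG is then a predictor of an outcome that can include that same value.
- Arm defines the tables, but whether it belongs to the predictors meant by the model sentence is unclear. If it does not, no IgG model compares the arms at all.
- Prior use of either drug is the union of two other listed predictors, so the three coefficients are hard to interpret together.

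At stake is how a null result is read. The model will report estimates, confidence intervals and P-values. A non-significant arm effect, or the absence of one, could be taken as reassurance about IgG when the model had little chance of showing a difference.

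**Working it through.** **Plan's own figure.** There is none for IgG. The sample size in Protocol 16.3 and SAP 7 concerns relapse only.

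**Inputs from the documents.** 160 patients randomised 1:1, so 80 per arm. Protocol Appendix 1 schedules immunoglobulins at 14 visits from month 0 to month 48. Four are at or before month 4 (0, 1.5, 3, 4). After month 4 there are 8, 9 or 10, according to whether the patient closes at month 36, 42 or 48.

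**Assumed inputs.** Normal IgG with mean 8–10 g/L, total SD σ of 2–2.5, within-patient correlation ρ of 0.7–0.8, random intercept, no drop-out.

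**Step 1: one measurement.** Cutting a normal variable where a proportion p falls below the cut keeps φ(z_p)²/[p(1−p)] of the information:

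| p | 5% | 10% | 20% | 30% | 50% |
|---|---|---|---|---|---|
| kept | 0.22 | 0.34 | 0.49 | 0.58 | 0.64 |

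More than half is lost only when about 20% or fewer fall below the cut.

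**Step 2: continuous analysis, uniform shift.** Take the mean of k = 9 post-month-4 values, adjusted for month 4 IgG. Its residual variance is V = σ²[ρ + (1−ρ)/k − ρ²], and the SE of the arm difference is √(2V/80).

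- Weakest corner (σ = 2.5, ρ = 0.7, shift 0.4): V = 6.25 × (0.7 + 0.033 − 0.49) = 1.52; SE = 0.195; z = 0.4/0.195 = 2.05; power = Φ(2.05 − 1.96) = 54%.
- Strongest corner (σ = 2, ρ = 0.8, shift 0.6): V = 4 × (0.8 + 0.022 − 0.64) = 0.73; SE = 0.135; z = 4.44; power above 99%.

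**Step 3: ever/never model, same shift, by simulation.** Arm is included as a predictor, which is generous to the SAP.

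- Mean 8–10, shift 0.4–0.6 g/L: 4–35% for ever/never, 59–100% for the month-4-adjusted mean. The closed form in step 2 puts the lower end at 54%.
- Mean 8–9, shift 0.6 g/L: 22–40% with the SAP's definition (induction values counted, month 0 IgG adjusted); 30–51% with post-month-4 values only and month 4 IgG adjusted; 84–100% for the month-4-adjusted mean. Counting induction values costs something, but most of the gap comes from the cut.

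**Step 4: fall confined to a minority.** Either 20% of rituximab patients lose 4 g/L or 30% lose 3 g/L, building up over 20 months (mean 8–10, SD 2–2.5, ρ 0.6–0.8, both analyses adjusted for month 0 IgG). Power was 29–80% for ever/never against 65–98% for the continuous mean. Scenario by scenario the gap ran from 16 points (75% against 91%) to 42 points (41% against 83%). The binary model kept 28–67% of the information. Simulations of this pattern with the continuous analysis adjusted for month 4 IgG gave 42–89% against 88–100%.

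**Step 5: single-visit contrasts.** Steps 2 to 4 concern the average over visits. At one visit the residual variance is σ²(1 − ρ²).

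- Weakest corner: 6.25 × 0.51 = 3.19, SE 0.282, z = 1.42, power 29%.
- Strongest corner: 4 × 0.36 = 1.44, SE 0.190, z = 3.16, power 89%.

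The average over visits should therefore be reported beside any single-visit difference.

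**The case against.** **The analysis is exploratory.** The SAP says so. IgG is not among the secondary endpoints in SAP 5.2.2, and no confirmatory conclusion rests on the model. This stands and limits the weight of the point. It does not make a low-powered model informative.

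**A threshold event is a legitimate target.** IgG below 5 g/L is a protocol-selected adverse event (Protocol 13.3) and is reported to the DSMB (Protocol 13.4.2). The model's stated aim is to predict that event. This stands, and is why the threshold tables and the logistic model should stay.

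**A uniform shift favours a mean.** True. Step 4 uses a pattern kinder to the threshold; the gap shrinks but does not close.

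**Later IgG can be altered by earlier low IgG,** through IVIg (Protocol 13.3.1) or a rituximab dose not given (Protocol 11.1.6). This stands as a limit on interpretation. It can be met by stating that all values are used regardless, with a sensitivity analysis.

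**Visit numbers differ between patients.** They follow enrolment date, which randomisation balances, so this does not bias the arm comparison.

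A reader might infer three stronger things that the documents do not support:

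- That most of the IgG information is discarded. Continuous IgG is summarised and plotted by arm, and new values below 3 g/L are counted. The loss is confined to the model, and its size depends on a distribution the documents do not give.
- That low IgG is rituximab's main long-term immunological risk. The protocol does not say this; Protocol 7.3.1 reports no significant fall in immunoglobulins in the pilot cohort.
- That the logistic model has too few events for its predictors. Under the assumed ranges the number of cases runs from about 7 to 71 of 160, so no events-per-coefficient figure can be defended.

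**Conclusion.** The concern holds as a gap in an exploratory safety analysis. The only IgG model uses a binary outcome, includes values that arm cannot affect, and leaves the role of arm unclear. Continuous serial IgG has no inferential analysis.

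For a uniform arm shift of 0.4–0.6 g/L, power is about 4–40% with the ever/never model and about 54–100% with a month-4-adjusted mean. At 0.6 g/L and mean 8–9 the gap is at least 84 − 40 = 44 points. With a fall confined to a minority it is about 16–42 points.

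The direction was the same in every pattern examined. The sizes rest on the assumed mean, SD, correlation and effect pattern, and the documents attach no clinical meaning to a difference of 0.4–0.6 g/L.

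**What to change.** In SAP 11.3:

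1. Add an exploratory linear mixed model of IgG (g/L) at scheduled visits after month 4, with arm, visit, arm by visit, month 4 IgG, the three stratification factors, and prior rituximab and prior cyclophosphamide.
2. Report adjusted arm differences with 95% CIs at months 24 and 36, and the average over visits. Use all values regardless of IVIg or withheld doses. Add a sensitivity analysis that excludes values after IVIg.
3. Keep the tables and counts for IgG below 5 and below 3 g/L.
4. Keep the logistic model as supportive. Limit its outcome to new IgG below 5 g/L after month 4, name treatment arm as a predictor, and do not enter prior use of either drug together with its two components.

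The cost is SAP wording and one model on data already collected. A mean difference is less directly clinical than a threshold, and later IgG may reflect IVIg or withheld rituximab. Items 2 and 3 address both.
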